5.2 Screening visit for the Interventional trial

All consecutive eligible patients should be approached for participation in the trial by the clinical investigators or person qualified to carry out the research. The clinical investigator will inform the eligible person then collect the free and written consent of the person undergoing to the research. If the patient is unable to provide consent within the time window allowed by the protocol, his or her authorized persons (members family, curator, guardianship, trusted person) may be approached in person. The local research team could also enroll eligible patients and obtain consent subsequently as per French national regulation under a deferred consent model.

To obtain informed consent, study personnel should follow the following steps:

- Present information on the study in a simple and understandable manner;
- Answer questions in a simple and understandable manner;
- Allow the potential participant/authorized persons an opportunity to reflect and discuss study participation with their family, friends, or family physician if desired;
- Confirm that the participant/authorized persons understands the risks and benefits of participating in the study and that their participation is voluntary;
- Complete and obtain signatures for informed consent form and obtain contact information from the participant/authorized persons.

Whose consent must be obtained	Who informs the individuals and collects their consent	At what point the individuals are informed	At what point the consent is obtained
Patient if able to understand and consent: "consentement patient" If patient not able to consent: Family member, close relative if present at the time of inclusion "consentement proche" or when they become	the principal investigator or collaborating physician declared and trained in the study (specify the specialist field)	 At the time of inclusion for patient if able to understand and consent If patient not able to consent: family member / close relative f patient not able 	 At the time of randomization for family member / close relative if one is present After randomization as soon as possible for
present "consentement proche poursuite" - If the patient is under guardianship: the guardian' consent is required : "consentement tutelle"		t After inclusion for patient unable to be informed at the time of inclusion and/or family member/ close relative as soon as possible if patient is unable to be informed	family member / close relative and/or patient as soon as his status allows
- If the patient is under curatorship: the curator must be informed of the study. The patient signs a consent form with the presence of the curator			

"consentement curatelle".		
Patient as soon as his status allows if he was not able toconsent on entry; "consentement de poursuite"		

5.3 Baseline visit and randomisation visit

- Verification of inclusion and exclusion criteria
- patient demographics, source of infection, severity of illness (SAPS II and SOFA scores) (Le Gall 1993 Vincent), pre-existing comorbidities as defined in the Charlson comorbidity index (addendum 15.4.2) (Charlson 1994), Clinical Frailty Scale (addendum 15.43) (Rockwood 2005; Bagshaw 2014; Muscedere 2017).
- Core temperature, vital signs, central hemodynamic data (if available)
- Standard laboratory data including serum and urinary electrolytes, creatinine, urea, cholesterol ,triglycerides and glucose levels, arterial lactate levels, arterial oxygen tension and hemoglobin oxygen saturation, arterial pH, white blood cell counts, hemoglobin and hematocrit levels, INR, platelets count, total bilirubin levels.
- Microbiolology and virology, i.e. blood and any potential source of infection will be sampled for bacterial culture, nasopharyngeal, bronchial, or broncho-alveolar lavage fluid will be sampled for testing byPCR for SARS-CoV-2 and any other respiratory virus
- Synacthen test, i.e. blood sample for cortisol measurement immediately before and 30 and 60 minutes after 250µg intravenous bolus of corticotrophin.
- Whole blood samples will be collected for measurements of biomarkers described in WP3 and WP4. These blood samples will be managed within WP2.
- Interventions: mechanical ventilation, renal replacement, vasopressors, unblinded corticosteroids, thiamine, vitamin C, other vitamins, nutrition, intravenous fluids, blood products, anticoagulants, sedatives, stress ulcer prophylaxis, and antimicrobials),

5.4 Follow-up visits

The patients included will be further followed for up to 180 days after randomization. Clinical and biological data will be assessed as described in table 4.1.19

Daily data until ICU discharge or 90 days (whichever comes first):

- a. Vital status
- b. protocol adherence (receipt of every planned dose until completion of 7 days treatment protocol),
- c. co-interventions (administration of mechanical ventilation, renal replacement, vasopressors, unblinded corticosteroids, thiamine, vitamin C, other vitamins, nutrition, intravenous fluids, blood products, anticoagulants, sedatives, stress ulcer prophylaxis, and antimicrobials),
- d. core temperature (lowest and highest of the day), vital signs (lowest and highest values for heart rate, systolic and diastolic blood pressure) and whenever needed central hemodynamic data (one per day),

standard laboratory data including serum and urinary electrolytes, creatinine, urea, cholesterol, triglycerides and glucose levels, arterial lactate levels, arterial oxygen tension and hemoglobin oxygen saturation, arterial pH, white blood cell counts, hemoglobin and hematocrit levels, INR, platelets count, total bilirubin levels.

- e. Sampling for microbiology or virology will be collected at Day 1, and 7, and additional sampling will be left at physicians' discretion
- f. Whole blood samples will be collected at Day 1 and Day 7 for measurements of biomarkers described in WP3 and WP4. These blood samples will be managed within WP2.

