1.3 CORTICOSTEROIDS AND SEPSIS

Researchers have explored the biological mechanisms of sepsis to explore potential interventions. Corticosteroids have been a topic of particular focus because of their influence on the immune response (Cain 2017). In sepsis, the hypothalamic-pituitary gland hormonal pathway to the adrenal glands stimulates corticosteroid production (Annane 2017a: Chrousos 1995: Cooper 2003: Heming 2018). These hormones affect inflammation through production of white blood cells, cytokines (proteins that influence the immune response) and nitric oxide. In sepsis, cytokines may suppress adrenocorticotropin hormone synthesis (Annane 2017a; Polito 2011; Sharshar 2003), and the cortisol response to exogenous adrenocorticotropin hormone (Annane 2017a; Hotta 1986; Jaattela 1991). Likewise, sepsis may be associated with alterations in scavenger receptor B1-mediated cholesterol delivery (Cai 2008). This causes poor adrenal activity in almost half of patients (Annane 2000; Lipiner 2007; Marik 2008; Rothwell 1991), and possible resistance of body tissues to corticosteroids (Meduri 1998a), due to fewer corticosteroid receptors or receptors with lower affinity (Barnes 1995; Huang 1987; Molijn 1995). Alteration in corticosteroid receptor numbers and in binding capacity may be related at least in part to nitric oxide (Duma 2004; Galigniana 1999). Recent works suggest that immune cells - not steroid-secreting cells - are key regulators of the interaction between the immune sytem and the adrenals (Kanczkowski 2013). In addition, acute illness such as sepsis may be associated with decreased cortisol clearance from plasma (Boonen 2013; Melby 1958), likely resulting from altered hepatic and renal inactivation of cortisol (Boonen 2013), Early studies showed that a pharmacological dose of corticosteroids prolonged survival among animals with sepsis (Fabian 1982). More recent studies in rodents have demonstrated that lower doses of corticosteroids, for example, 0.1 mg/kg of dexamethasone, improved haemodynamic and organ function, favourably modulated the inflammatory response and prolonged survival (di Villa Bianca 2003; Heller 2003; Tsao 2004; Vachharajani 2006). Protective effects of these glucocorticoids against sepsis may be mediated in part by the endothelial glucocorticoid receptor (Goodwin 2013). In healthy volunteers challenged with endotoxin, a low dose of corticosteroids, for example, 10 mg of prednisolone, blocked the release of pro-inflammatory cytokines, prevented endothelial cell and neutrophil activation and inhibited the acute phase response without altering coagulation and fibrinolysis balance (de Kruif 2007). Studies in patients with septic shock showed that a short course of corticosteroids may result in a rebound in the systemic inflammatory response (Briegel 1994; Keh 2003). In addition, it is now recognized that increased pro-inflammatory cytokine release can be sustained for longer than a week in patients with sepsis (Kellum 2007). Likewise, timing of initiation of corticosteroids may be an important factor in response to treatment. Indeed, in observational studies, short-term mortality increased with delayed initiation of hydrocortisone (Katsenos 2014; Park 2012). For these reasons, we would anticipate that corticosteroid treatment is

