5.5 Last study visit

At 6 months, follow-up will be achieved by telephone by the Coordinating Centre.

- At 90- and 180-day data:
 - a. Vital status
 - b. Location: still ICU (or date discharge), hospital ward (or date discharge), rehabilitation centre, long-term facility, home (date discharge to home)
 - c. co-interventions: mechanical ventilation (or date weaned off), renal replacement (or date weaned off), vasopressors (or date weaned off)
 - d. core temperature (lowest and highest of the day), vital signs (lowest and highest values for heart rate, systolic and diastolic blood pressure) if still at hospital
 - e. Glasgow coma scale Cognitive function
 - f. MDRS score
 - g. HRQoL, promis

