5.8 Table or diagram summarising the chronology of the study

							Da	ays						6 months
	0	1	2	3	4	5- 6	7	8- 9	10	11- 13	14	28	90	
Verification of inclusion and exclusion criteria	X													
Informed consent	Х													
Source of infection		х												
Severity of illness (SAPS II score)		x												
Sepsis data		х												
Pre-existing comorbidities (Charlson comorbidity index, Clinical Frailty Score)		x												
Randomization* (Interventional phase)		х												
Dispensation of treatments		X	X	Х	X	Х	Х							
Biological samples<	Х	Х	x	х	х	х	х	х	x	х	х	x		
Additional Biological samples (biomarqueurs)	X	Xa					X							
Protocol adherence ^b		х	Х	Х	Х	Х	Х							
Co-interventions ^c		Х	Х	х	х	Х	х	Х	х	х	Х	Х	х	
Death or persistent organ dysfunction ^d		х	x	x	х	х	x	х	х	х	x	х	х	x
Vasopressor dependency		х	x	x	х	х	x	х	х	х	x	Х	х	
Organ function including renal function (SOFA score)*	Х	x	x	X	X		X		x		X	x		
HRQoL (EQ-5D-5L) ^e , Promis		x										х	х	x
Serious adverse events*		x	Х	Х	Х	х	x	х	х	х	х	х	x	X

^aMust be collected before the first dose of investigational product. Samples include blood, urine, cells, exhaled air

^bReceipt of every planned dose according to schedule until completion of 7-day treatment protocol, samples collected per protocol instructions, biomarkers collected before the first dose of investigational product.

^cAdministration of mechanical ventilation, renal replacement, vasopressors, vitamin C, thiamine, intravenous fluids, blood products, sedatives, and antimicrobials. Daily data until ICU discharge or 28 days (whichever comes first).

^dDependency on mechanical ventilation, renal replacement, or vasopressors. eEQ5D to be filled at 3 and 6 months

* Interventional trial

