5.11.4 POSOLOGY AND DRUGS ADMINISTRATION

Initiation of treatments:

Treatment should be started immediately after randomization (day 0 of the study).

Posology:

- Hydrocortisone hemisuccinate /placebo will be given as 50 mg intravenous bolus every 6 hours

- Fludrocortisone /placebo* will be given as a 50 µg tablet via a nasogastric tube once per day in the morning

* Patients with COVID-19 will receive only experimental fludrocortisone or its placebo AND NOT hydrocortisone or its placebo as they will receive dexamethasone as the standard of care.

Duration of treatments:

Study drugs will be given until the patient will be discharge from the ICU for a maximal treatment duration of 7 days for steroids. Study drugs will be stopped without tapering off.

Reconstitution for IV injection of hydrocortisone/placebo:

Hydrocortisone hemisuccinate lyophilisate will be reconstituted prior to use with 2 mL water for injection. The solvent must be injected gently into the vial. Reconstitution and dilution should be performed in accordance with Good Clinical Practices guidelines, particularly with respect to asepsis and to Hydrocortisone SmPC. Hydrocortisone must not be used if the reconstituted solution has a cloudy appearance or contains floccular or particulate matter. The SmPC instructions for use, handling and disposal should be strictly followed.

The volume injected will be 1 mL, containing 50 mg of Hydrocortisone.

"Administration of fludrocortisone/placebo

A 50 μ g fludrocortisone/Placebo tablet is administered, enterally, once a day. For patients with a nasogastric tube, the entire tablet will be introduced into the nozzle of the tube. The tube will be flushed with 50 mL of water (the 10 first mL have to be injected slowly) and clamped for at least 30 minutes after tablet administration."

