5.14.2 Secondary Outcomes

The secondary outcomes will include:

1) Mortality at 7, 14, 28 day and 6 months.

2) Vasopressor free days: defined as the number of days with permanent hemodynamic stability in the absence of any vasopressor agent, norepinephrine, phenylephrine, epinephrine, dopamine, vasopressine or its analogs, and soever. When a patient will die on vasopressor therapy, the corresponding vasopressor free day will be 0.

3) Mechanical ventilation free days: defined as the number of days with permanent appropriate oxygenation while the patients is extubated and breathing spontaneously, i.e. no need for non invasive ventilation, high flow oxygen or CPAP. Other uses of non-invasive ventilation (e.g., chronic night-time use for chronic obstructive pulmonary disease) are not counted. When a patient will die on mechanical ventilation or will be discharge home on mechanical ventilation, the corresponding mechanical ventilation free day will be 0.

4) Organ dysfunction free days: Organ function (including renal function) will be assessed by the SOFA score (Vincent 1996). Organ dysfunction will be defined by a SOFA score of > 6 (Annane 2018). Organ dysfunction free days are defined by the number of days with os total SOFA score of 6 or less. When a patient will die on vasopressor therapy, the corresponding vasopressor free day will be 0.

5) HRQoL in 6-month survivors assessed by the EuroQol-5D (EQ-5D). This questionnaire is a standardised measure of health status developed to provide a simple, generic measure of health for clinical and economic appraisal. It is made up for two components; health state description and evaluation. The health status is measured in terms of five dimensions; mobility, self-care, usual activities, pain/discomfort, and anxiety/depression. In evaluation part, the respondents evaluate their overall health status using the visual analogue scale. See Figure 4.

6) Proportion of patients with a decision to withhold and/or withdraw active treatments

7) ICU and hospital length of stay

8) Rate of re-admission to the ICU during the 180 days after randomization

9) Safety endpoints:

- Proportion of patients affected by any serious adverse events associated with corticosteroids, among the following: hospital-acquired infections, hyperglycemia, hypernatremia, neurological disorders (coma, stroke or muscle weakness, as defined below) during the 90 days after randomization
- Coma will be defined as a Glasgow coma score < 8

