5.15 Data Collection and Participant Follow-up

Potential participants will be referred to the research team by intensivists and other ICU staff. The research team will confirm eligibility and the site principal investigator and co-investigators will confirm whether the patient or others authorized persons may be approached for consent. If that is the case, the research team will obtain consent from the patient or others authorized persons or will enroll and obtain consent subsequently as a deferred consent model

Daily data will be collected from day 1 until day 90 (or at the time of ICU discharge). At 6 months, followup will be achieved by telephone by the Coordinating Centre. Table 5.1.8 describes requirements and procedures at each follow-up time point. All study outcomes (as defined in sections 8.1 and 8.2) will be documented on the electronic CRFs (eCRF).

Time points:

- 1) Baseline data:
 - a. patient demographics, source of infection, severity of illness (SAPS II and SOFA scores) (Le Gall 1993), pre-existing comorbidities as defined in the Charlson comorbidity index (Table 3) (Charlson 1994), Clinical Frailty Scale (Table 4) (Rockwood 2005; Bagshaw 2014; Muscedere 2017).
 - b. Core temperature, vital signs, central hemodynamic data (if available)
 - c. Standard laboratory data including serum and urinary electrolytes, creatinine, urea, *cholesterol*, *triglycerides* and glucose levels, arterial lactate levels, arterial oxygen tension and hemoglobin oxygen saturation, arterial pH, white blood cell counts, hemoglobin and hematocrit levels, INR, platelets count, total bilirubin levels.
 - d. Microbiology and virology, blood and any suspected soure of infection will be sampled, nasopharyngeal, bronchial or broncho-alveolar lavage fluids will be tested by PCR for SARS-CoV-2 and other respiratory viruses.
 - e. Synacthen test, i.e. blood sample for cortisol measurement immediately before and 30 and 60 minutes after 250µg intravenous bolus of corticotrophin.
 - f. Whole blood samples will be collected for measurements of biomarkers described in WP3 and WP4. These blood samples will be managed within WP2.
 - g. Interventions: mechanical ventilation, renal replacement, vasopressors, unblinded corticosteroids, thiamine, vitamin C, other vitamins, nutrition, intravenous fluids, blood products, anticoagulants, sedatives, stress ulcer prophylaxis, and antimicrobials),

2) Daily data until ICU discharge or 90 days (whichever comes first):

- a. Vital status

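### Daily organ-support data stop at ICU discharge, with conflicting outer limits of day 28 and day 90, and nothing records support or ICU stay after a readmission

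*Protocol*

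**What the plan says.** **Daily record.** Section 5.4 sets the span for co-interventions: "Daily data until ICU discharge or 90 days (whichever comes first". Section 5.15 agrees: "Daily data will be collected from day 1 until day 90 (or at the time of ICU discharge". Sections 6.1 and 6.2 give the same day-90 limit. Footnote c in section 5.8, attached to the co-interventions row, differs: "Daily data until ICU discharge or 28 days (whichever comes first". That same row carries a mark at day 90.

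**Later contacts.** At days 90 and 180, sections 5.5 and 5.15 ask for "Location: still ICU (or date discharge), hospital ward (or date discharge), rehabilitation centre, long-term facility, home (date discharge to home" and for "co-interventions: mechanical ventilation (or date weaned off), renal replacement (or date weaned off), vasopressors (or date weaned off". Each type of support has a status or a single weaning date.

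**Outcomes that need these data.** Section 5.14.2 defines vasopressor-free days (item 2) by permanent haemodynamic stability off all vasopressors, and ventilation-free days (item 3) in a similar way. Item 8 is "Rate of re-admission to the ICU during the 180 days after randomization". Sections 9.1 and 9.2.1 make vasopressor-free days to day 28 the efficacy measure of the sequential analyses.

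**The concern.** A count of support-free days to day 28 needs to know, for each of the 28 days, whether support was given. The protocol secures this only while the patient remains in the ICU. A patient who leaves, deteriorates and returns to the ICU on vasopressors or a ventilator before day 28 spends days on support that no listed item captures day by day. Unless someone recovers those days, they may be counted as free.

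Two outcomes are directly exposed: vasopressor-free days, which feed decisions on whether biomarker cohorts continue, and ventilation-free days. A third, ICU readmission to day 180, appears on no visit list and in no schedule row. Separately, sites are given two different end dates for the same daily items and could follow either. An analysis plan can set scoring rules, but it cannot supply days that were never recorded.

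**Working it through.** **1. The protocol's own figure.** Section 9.1 states 80.04% power with 176 patients per arm for a difference of 3 days, SD 10, alpha 0.05, two-sample t-test. The noncentral t calculation, two-sided, gives 80.14%. The figure reproduces, so the point concerns data collection and not the sample-size arithmetic.

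**2. What each source can supply after ICU discharge.**

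| Source | Supplies | Does not supply |
|---|---|---|
| Daily data (5.4, 5.15, 6.1, 6.2) | Nothing after discharge | Any day of a readmission |
| Footnote c (5.8) | Nothing after discharge or day 28 | The same, plus daily co-intervention data from day 28 to day 90 |
| Vasopressor dependency row (5.8) | Marks at days 8-9, 10, 11-13, 14, 28 and 90 | Days 15 to 27, which have no column |
| Day-90 and day-180 lists (5.5, 5.15) | Location, status or one weaning date | Restart date, number of days, readmission |

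**3. One hypothetical patient.** Suppose the last vasopressor day is day 8, ICU discharge is on day 8, and a readmission brings vasopressors on days 16 to 22 (7 days). The checks at days 14 and 28 are both negative.

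- No record of the relapse: 28 - 8 = 20 free days.
- Relapse days recorded and counted as not free: 20 - 7 = 13.
- Permanent stability read strictly, counting only after the last stop: 28 - 22 = 6.

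The choice between 13 and 6 is a scoring matter. Getting away from 20 requires restart and stop dates that no list contains.

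**4. Effect on the arm difference.** Let rA and rB be the shares relapsing after discharge in the active and placebo arms, and d the missed vasopressor days before day 28, taken as equal in both arms. Each arm's mean is overcounted by r x d, and the difference shifts by (rA - rB) x d. The protocol gives none of these quantities, so the values below are assumptions.

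| rA vs rB | d = 3 | d = 10 |
|---|---|---|
| 5% vs 2% | 0.03 x 3 = 0.09 day | 0.03 x 10 = 0.30 day |
| 10% vs 5% | 0.05 x 3 = 0.15 day | 0.05 x 10 = 0.50 day |
| 10% vs 2% | 0.08 x 3 = 0.24 day | 0.08 x 10 = 0.80 day |
| Equal | 0 | 0 |

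The range of 0.09 to 0.80 day is 3% to 27% of the planned 3 days (0.09/3; 0.80/3). It is 4% to 38% of the 2.1 days (17.1 - 15.0) that section 9.1 cites from the earlier trial. An observed 3 days would correspond to a true 2.91 to 2.20 days, for which 176 per arm gives 78% to 54% power. If placebo patients relapse more, the sign reverses.

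**The case against.** The strongest defence is that the protocol does not overlook these events. Readmission is a named outcome. Sections 5.15 and 6.1 promise that all outcomes go on the eCRF. Section 5.15 makes local teams responsible for data while patients are in hospital, not only in the ICU. Section 7.3.2 requires all adverse events to be recorded, and the schedule's serious adverse event row runs to 6 months, so relapsing shock would ordinarily leave a trace. This stands as far as it goes, but none of it yields a count of days or a dated readmission field. The promise in section 5.15 also points to sections 8.1 and 8.2 for the outcome definitions; these are committee sections.

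Four stronger readings are tempting, and the document does not support them.

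- *Relapse is scored as vasopressor-free.* No section says so. The requirement of permanent stability points the other way, and the scoring rule may sit in the SAP, which is not shown.
- *The loss favours the active arm.* Section 5.11.4 says "Study drugs will be stopped without tapering off", and section 1.3 notes that "a short course of corticosteroids may result in a rebound in the systemic inflammatory response". But treatment lasts at most 7 days, so stopping coincides with discharge only for patients who leave earlier. The cited rebound is inflammatory, not recurrent shock, and placebo patients can relapse too.
- *Cohort decisions are pushed towards benefit.* The efficacy criterion in section 9.2.1 is a ratio of subgroup effects. A similar overstatement in both subsets, with both effects positive, pulls that ratio towards 1.
- *Footnote c leaves dependency between days 28 and 90 unrecorded, damaging the primary outcome.* The footnote belongs to the co-interventions row only. The rows for vasopressor dependency and for death or persistent organ dysfunction are marked at day 90, and section 5.5 takes support status then.

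**Conclusion.** The point holds as a gap and an inconsistency in data collection. The day-28 and day-90 limits contradict each other; this needs no assumption. No section reopens the daily record on readmission, and no list holds a readmission item or a restart date; this too is read directly from the text. It follows that support-free days to day 28 may be overcounted for patients readmitted in that window, and that the 180-day readmission rate has no listed collection item.

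Whether the comparison between arms is biased, by how much and in which direction cannot be derived from the document. The 0.09 to 0.80 day range rests entirely on assumed imbalances of 3 to 8 percentage points and 3 to 10 missed days, and it is zero if relapse is equal. The day-90 primary outcome is not shown to be affected. The change is worth making because it is cheap and because unrecorded days become harder to recover later.

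**What to change.** - In sections 5.4, 5.15, 6.1 and 6.2, require daily organ-support data on every ICU day, including readmissions, to day 90.
- Align footnote c in section 5.8 with that limit.
- Add dated eCRF fields for ICU readmission to day 180, and for restart and stop of vasopressors, ventilation and renal replacement. Complete the support fields from hospital records at day 28 and day 90, so that the sequential analyses do not wait for the day-90 contact. Add the readmission item to the day-90 and day-180 lists.
- State that days on restarted support count as not free.

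The cost is a few eCRF fields, revised schedule wording and chart review for the patients who are readmitted. Data will remain incomplete for readmissions to non-participating hospitals. No treatment or visit changes.
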